5.7. Antihypertensive Medications

The mean number of antihypertensive medications will be summarized at baseline, 8 weeks, 6 months, 1 year and 2 years. The number and percentage of patients on 0 to 3, and >3 medications will additionally be presented. The mean change from baseline in the number of antihypertensive medications at each visit will be presented along with the matched baseline mean values. Antihypertensive medications will also be summarized by class. These analyses will be conducted in the ITT Analysis Set.

5.8. Adverse Experiences

5.8.1. Adverse Events

Adverse events will be coded using the Medical Dictionary for Regulatory Activities (MedDRA) per the data management plan for the study. Summary statistics for AEs will be presented by MedDRA system organ class and preferred term.

Treatment-emergent AEs (TEAEs) are defined as AEs that meet one of the following criteria:

- Have a start date and time during or after the procedure
- Have a missing start date, and the stop date is after the procedure

• Have a start date and time before the procedure, but have a worsening severity during or after the procedure.

Overall summary statistics (number of events, and number and percentage of subjects) will be prepared by treatment group for the following treatment-emergent events: TEAEs, related TEAEs, SAEs, related SAEs, MAEs, related MAEs (per investigator and CEC adjudication), AEs leading to study discontinuation, AEs leading to procedure interruption/discontinuation, and deaths.

Related AEs are those AEs that are recorded as being related to the study procedure/treatment. Events for which the relationship is not recorded will be considered as related for the purpose of the tabular summaries.

Rates of AEs (serious and non-serious), peri-procedurally, at discharge, and at each of the follow-up time points will be summarized cumulatively as follows:

- Frequency (number and percentage of subjects) with TEAEs, overall and by MedDRA system organ class and preferred term
- Frequency (number and percentage of subjects) with treatment-emergent SAEs, overall and by MedDRA system organ class and preferred term
- Frequency (number and percentage of subjects) with each site-reported treatment-emergent AE or SAE, by relationship to the investigational device or procedure according to both the investigator and the CEC (SAEs only)
- Frequency (number and percentage of subjects) with each site-reported treatmentemergent AE or SAE, by severity.

These analyses will be conducted in the Safety Analysis Set.

AEs and SAEs that start before the procedure (i.e. which are not treatment-emergent) will also be listed for all enrolled subjects, including screen failures.

5.8.1.1. Listing of Adverse Events by Patient

A by-patient listing of all adverse events reported, including date started/stopped, seriousness, intensity, relationship to study drug, action taken, and outcome will be presented in the data listings. TEAEs will be flagged in the listing.

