	
in the protocol). After 8 weeks, antihypertensive medications are permitted according to the protocol-defined criteria and proposed titration scheme.
 
Follow-up visits will be performed at 4 weeks, 8 weeks, 3 months, 6 months, 1 year, and 2 years.
 
The study will be unblinded after the last subject has completed the 1-year follow-up visit.
 
Crossover from the Sham Control Arm to the Treatment Arm may be allowed, at the discretion of the treating investigator, after the Data Safety Monitoring Board (DSMB) has reviewed the 1-year data from all subjects and the study has been unblinded.

Study Geography/ Number of Planned Investigational Sites	United States (US) and Europe Multicenter trial with approximately 25 investigational sites (in the US and Europe)
Number of Groups/ Arms/Cohorts	2 groups (Treatment Arm, Sham Control Arm; randomized 1:1)
Number of Targeted Subject Treatment, Total and in Each Arm	Approximately 90 subjects randomized: 
 • 45 subjects in the Treatment Arm • 45 subjects in the Sham Control Arm
Planned Duration of Subject Participation	Approximately 26 months* (for each subject) 
 • Screening period: approximately 4 to 8 weeks • Run-in period: 4 weeks • In-hospital period: 2 days • Follow-up period: 2 years 
*May be different for subjects in Sham Control Arm in the case of crossover: subjects will have a final 1-year follow-up visit after crossover treatment.

INVESTIGATIONAL PRODUCT(S), DOSE AND MODE OF ADMINISTRATION	
Active Product	
Combination Product: Peregrine System Kit
 
Drug Constituent Part: Dehydrated Alcohol Injection, USP
 
Device Constituent Part: Peregrine System Infusion Catheter
 
Dose: 0.6 mL alcohol per treated renal artery. Maximum total dose per subject = 2.4 mL at one treatment session (i.e. during the same procedure).
 
Dosage form: Solution for injection
 
Dosage frequency: Once during the study procedure
 
Mode of administration: Direct infusion to the perivascular space, during an endovascular procedure using the device constituent part

Placebo/Control/ Comparator	
In the Sham Control Arm, only renal angiography will be performed. No alcohol infusion (i.e. no renal denervation) will be performed.
 
Dosage form: Not applicable
 
Dosage frequency: Once during the study procedure
 
Mode of administration: Endovascular

SUBJECT SELECTION

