5.2. General Considerations

5.2.1. General Methods

Two unblinded team members (either two statisticians or a statistician and a statistical programmer) will be assigned for all analyses. This will allow for discussion of output and direct QC of statistical programming on the exact same dataset.

In general, continuous variables will be summarized with descriptive statistics (n, mean, SD, range, median, and interquartile range). The difference between groups will be presented and the normal approximation will be used to calculate two-sided 95% confidence intervals (CIs). Change from baseline, when relevant, will be computed as the paired mean difference and 95% CI of the mean difference at each time point.

For all continuous primary and secondary blood pressure endpoints, changes over time will be additionally explored in mixed effects repeated measures analyses, including the values at all time points.

Categorical variables will be summarized as frequencies and percentages. Relative risks and 95% CIs will be computed.

All statistical analyses will be performed using SAS® Version 9.4 or higher (SAS Institute, Cary, NC 27513, USA).

For each variable, the baseline value will be defined as the last value collected before the procedure.

There will be no formal hypothesis testing conducted in the study. Ninety-five percent CIs, when presented, are intended to be descriptive in nature only. For binary variables, CIs will be calculated via exact binomial methods. For continuous variables, the CI of the mean will be constructed using the normal approximation.

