5.2.3. Handling of Dropouts or Missing Data

For the primary efficacy endpoint analysis, all available data will be used. As additional analyses, patients who meet the protocol defined criteria for antihypertensive drug treatment within the 8 weeks prior to assessment of the primary endpoint will be assigned their baseline value of ABPM at 8 weeks. Additional sensitivity analyses will be conducted removing those

subjects who receive antihypertensive treatment within 8 weeks. Also, as a secondary sensitivity analysis, missing data will be imputed via multiple imputation techniques.

There will be no imputation of data for secondary efficacy endpoints or other endpoints; only available data will be used, with the exception of analyses at 8 weeks for subjects receiving protocol defined antihypertensive therapy within 8 weeks. Analyses will be conducted with all available data and only in subjects who did not receive antihypertensive treatment between baseline and 8 weeks.

This study allows for cross-over of control subjects once the participant has passed the 1-year study visit. Subjects who cross-over will be considered withdrawn from the main study as of the day of their cross-over procedure and will no longer be analyzed with the main study cohort (i.e., their data will be missing for any subsequent scheduled study visits).

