Table 14.2.6-3 Antihypertensive Medication Use EMERGENCY USE MEDICATIONS, by baseline daytime ambulatory SBP >140 mmHg and DBP <90 mmHg - ITT Analysis Set

Table 14.2.7-1 Antihypertensive Medication Use beyond 8 weeks - ITT Analysis Set

Table 14.2.7-2 Antihypertensive Medication Use beyond 8 weeks - PP Analysis Set

Table 14.2.8-1.1 Office Systolic Blood Pressure at all time points - ITT Analysis Set

Table 14.2.8-1.2 Office Diastolic Blood Pressure at all time points - ITT Analysis Set

Table 14.2.8-2.1 24-Hour Systolic ABP at all time points - ITT Analysis Set

Table 14.2.8-2.2 24-Hour Diastolic ABP at all time points - ITT Analysis Set

Table 14.2.8-3.1 Daytime Systolic ABP at all time points - ITT Analysis Set

Table 14.2.8-3.2 Daytime Diastolic ABP at all time points - ITT Analysis Set

Table 14.2.8-4.1 Nighttime Systolic ABP at all time points - ITT Analysis Set

Table 14.2.8-4.2 Nighttime Diastolic ABP at all time points - ITT Analysis Set

Table 14.2.9 Anti-Hypertensive Medications at all time points by Class - ITT Analysis Set

Table 14.2.10 Anti-Hypertensive Medication Compliance 1 - ITT Analysis Set

Safety

Table 14.3.1-1 Summary of Treatment Emergent Adverse Events (TEAE) – Safety Analysis Set

Table 14.3.1-2.1 Treatment Emergent Adverse Events at any time during the study, by Relationship - Safety Analysis Set

Table 14.3.1-2.2 Treatment Emergent Adverse Events Peri-procedural, by Relationship - Safety Analysis Set

Table 14.3.1-2.3 Treatment Emergent Adverse Events through Discharge, by Relationship - Safety Analysis Set

- Table 14.3.1-2.4 Treatment Emergent Adverse Events within 8 weeks, by Relationship Safety Analysis Set
- Table 14.3.1-2.5 Treatment Emergent Adverse Events within 6 months, by Relationship Safety Analysis Set
- Table 14.3.1-2.6 Treatment Emergent Adverse Events within 1 Year, by Relationship Safety Analysis Set
- Table 14.3.1-3.1 Treatment Emergent Adverse Events at any time during the study, by Severity Safety Analysis Set
- Table 14.3.1-3.2 Treatment Emergent Adverse Events Peri-procedural, by Severity Safety Analysis Set
- Table 14.3.1-3.3 Treatment Emergent Adverse Events through Discharge, by Severity Safety Analysis Set
- Table 14.3.1-3.4 Treatment Emergent Adverse Events within 8 weeks, by Severity Safety Analysis Set
- Table 14.3.1-3.5 Treatment Emergent Adverse Events within 6 months, by Severity Safety Analysis Set

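### If sham subjects cross over before 2 years, the overall and any-time adverse event tables compare crude counts and percentages over unequal follow-up

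*SAP*

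**What the plan says.** **Adverse event summaries.** SAP 5.8.1 states: "Overall summary statistics (number of events, and number and percentage of subjects) will be prepared by treatment group". It sets no time cut-off and no person-time denominator. The period summaries are cumulative and begin with "Frequency (number and percentage of subjects) with TEAEs, overall and by MedDRA system organ class and preferred term". For categorical variables SAP 5.2.1 adds: "Relative risks and 95% CIs will be computed".

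**Table list.** SAP section 9 lists Table 14.3.1-2.1, "Treatment Emergent Adverse Events at any time during the study, by Relationship - Safety Analysis Set", and five tables with the same open horizon: 14.3.1-3.1, 14.3.2-1.1, 14.3.2-2.1, 14.3.3-1.1 and 14.3.3-2.1. The fixed-time adverse event tables stop at 1 year. The only time-to-event safety output is Figure 6 in SAP section 11, for adjudicated MAEs.

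**Crossover.** SAP 5.2.3: "This study allows for cross-over of control subjects once the participant has passed the 1-year study visit". It goes on: "Subjects who cross-over will be considered withdrawn from the main study as of the day of their cross-over procedure", and they "will no longer be analyzed with the main study cohort (i.e., their data will be missing for any subsequent scheduled study visits". No such cut applies to treated subjects, whose planned follow-up is 2 years.

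**Timing.** The protocol 7.0 synopsis (Study Design) allows crossover "after the Data Safety Monitoring Board (DSMB) has reviewed the 1-year data from all subjects and the study has been unblinded". SAP 3.2 instead has unblinding after the last 6-month visit, with crossover after DSMB review of 6-month data once the subject has had the 1-year visit. SAP section 2 says the SAP is based on protocol 6.0.

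**After crossover.** Protocol Table 2 (footnote 12) keeps recording adverse events through the crossover phase. SAP 4.1 groups the Safety Analysis Set by treatment actually received. The only crossover-phase table that SAP section 9 lists is disposition.

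**The concern.** A crude percentage with any event, or a crude event count, grows with time observed. If one arm's observation can be shortened and the other's cannot, the two figures differ even when the underlying risk is the same. Here the shortening can fall only on sham, so the treated arm would look worse.

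This touches a stated objective. Chronic safety is to be assessed up to 2 years (protocol synopsis; SAP 3.1). In the SAP's table list, general adverse events after 1 year appear only in the overall summary (Table 14.3.1-1) and the six any-time tables, and these are the outputs with unequal follow-up.

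**Working it through.** **The plan's own figures.** The documents state no adverse event rate, crossover share or exposure, so there is nothing on this point to reproduce. Their one power figure (80% for 5.1 mmHg, SD 8, 80 evaluable) recomputes to 80.4% with the noncentral t on 78 df, but it is not an input here.

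**Inputs from the documents.** Treated follow-up 24 months. Earliest crossover after the 1-year visit, controls only. Initiation May 2018 and primary endpoint completion June 2021 (protocol synopsis).

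**Assumptions.**
- First randomisation in August 2018, which is initiation plus up to 12 weeks of screening and run-in. Last randomisation in April 2021, 8 weeks before June 2021. Enrolment uniform over those 32 months.
- Equal, constant hazard in both arms, with 1-year risk r of 10%, 20% or 40%.
- Every sham subject still short of 24 months crosses as soon as allowed. Crossover opens 0 or 3 months after the qualifying last visit.

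**Formulas.**
- Treated 2-year risk: 1 − (1 − r)².
- Sham: the average of 1 − (1 − r)^T, with T the years to crossover, or 2 if not cut.
- Event-count ratio: 24 / mean sham months.

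**Protocol 7.0 condition, no lag.** Crossover opens 12 months after the last randomisation. Sham subjects randomised in the final 12 of 32 months can be cut: 12/32 = 37.5%. Their T is uniform on 12 to 24 months, mean 18. Mean sham follow-up = 24 − 0.375 × 6 = 21.75 months; event ratio 24/21.75 = 1.10.

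At r = 40% the treated risk is 1 − 0.6² = 64.0%. Among those cut, the mean risk is 1 − (0.6 − 0.36)/(−ln 0.6) = 53.0%. Sham overall is 0.375 × 53.0 + 0.625 × 64.0 = 59.9%, a difference of 4.1 points.

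**SAP 6-month unblinding, no lag.** The final 6/32 (18.75%) are cut at 12 months and a further 12/32 (37.5%) between 12 and 24 months. Mean sham follow-up = 24 − 0.1875 × 12 − 0.375 × 6 = 19.5 months; event ratio 24/19.5 = 1.23.

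| Crossover opens | Sham cut before 24 months | Mean sham months | Event ratio | Difference in points, r = 10 / 20 / 40% | Relative risk |
|---|---|---|---|---|---|
| Protocol 7.0, no lag | 12/32 = 37.5% | 21.75 | 1.10 | 1.7 / 2.9 / 4.1 | 1.07–1.10 |
| Protocol 7.0, 3-month lag | 9/32 = 28.1% | 22.73 | 1.06 | 0.9 / 1.6 / 2.2 | 1.04–1.05 |
| SAP 3.2, no lag | 18/32 = 56.25% | 19.50 | 1.23 | 3.3 / 5.9 / 8.6 | 1.16–1.21 |
| SAP 3.2, 3-month lag | 15/32 = 46.9% | 20.62 | 1.16 | 2.5 / 4.4 / 6.4 | 1.11–1.15 |

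At 50% uptake the differences are about half. With no crossover before 2 years they are zero.

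**After the fix.** Under equal constant hazard, Kaplan-Meier incidence censored at crossover has an expected ratio of 1.00 in every row.

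**Events per subject-year when risk is front-loaded.** Assume both arms have 1.0 event/year for 3 months, then 0.2/year, and 30% of sham cross at 1.25 years.
- Treated: 0.25 + 0.2 × 1.75 = 0.60 events over 2 years, or 0.300/year.
- Sham: 0.7 × 0.60 + 0.3 × 0.45 = 0.555 events over 0.7 × 2 + 0.3 × 1.25 = 1.775 years, or 0.313/year.

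The rate now flatters the treated arm by about 4%, while the crude event excess is 0.60/0.555, or 8%.

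**The case against.** **Crossover is optional and uptake is unknown.** This stands. A reader might infer that the treated arm is bound to show more events. The documents support only a conditional statement: crossover may be allowed, at the investigator's discretion, and nothing says how many will take it up.

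**The effect is small under protocol 7.0.** This also stands. Assuming 0.5 events per year and half of sham crossing at 1.25 years, treated is 1 − exp(−1) = 63.2% and sham 0.5 × 63.2 + 0.5 × 46.5 = 54.8%, a gap of 8.4 points with 23% more events. Under the enrolment assumed above, the protocol 7.0 condition leaves at most 37.5% of sham to be cut, at 18 months on average, so that scenario is out of reach. Even 4.1 points is about 1.8 of 45 subjects. The 95% half-width for 64.0% against 59.9% is 1.96 × √((0.64 × 0.36 + 0.599 × 0.401)/45), about 20 points. No test is planned on these tables. But the tilt runs in one direction, and descriptive figures are what readers will use to judge chronic safety.

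**Other outputs reach 2 years.** It would be too broad to say that nothing else does. Laboratory shift tables run to 2 years, by-patient adverse event listings are planned, and Figure 6 may extend that far for MAEs. SAP 5.8.1 also implies a summary at each follow-up point, though no 2-year table is listed, and a crude one would share the problem.

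**The adverse event cut-off is inferred.** SAP 5.2.3 deals with missing data and illustrates the cut by scheduled visits, while adverse events continue to be collected after crossover. This is fair, and it is a reason to write the rule down.

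**Conclusion.** The point holds conditionally. If any sham subject crosses before the 2-year visit, the overall TEAE/SAE summary and the six any-time tables are not a like-for-like comparison as written, and under equal hazards they lean against the treated arm.

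On the stated assumptions, with every eligible sham subject crossing, the size is 0.9–4.1 points and 6–10% more events under protocol 7.0. Under SAP 3.2 it is 2.5–8.6 points and 16–23% more events. Enrolment pattern, lag, uptake and event rate are all assumed. The peri-procedural, discharge, 8-week, 6-month and 1-year tables are unaffected, because crossover follows the 1-year visit. This is a modest bias that is cheap to remove and worth correcting before the 2-year analysis.

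**What to change.** - In SAP 5.8.1, state that sham adverse event follow-up is censored on the day of crossover and that later events are reported separately, in named crossover-phase tables.
- For summaries beyond 1 year, present Kaplan-Meier cumulative incidence to 2 years by arm, censored at crossover or withdrawal, with subject-years of follow-up shown.
- Use the existing 1-year tables (14.3.1-2.6, 14.3.1-3.6, 14.3.2-1.6, 14.3.2-2.6, 14.3.3-1.6 and 14.3.3-2.6) for the crude between-arm comparison and its relative risks.
- Events per 100 subject-years may be added as a supplement, labelled as unbiased only if the hazard is roughly constant, which may not hold after a one-time procedure.
- Reconcile the unblinding and crossover timing in SAP 3.2, 5.2.3 and 5.2.4 with protocol 7.0.

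The cost is SAP wording and programming from dates already collected. One limit remains: censoring at crossover assumes that subjects who cross have the same later risk as those who do not, and the report should say so.

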PROTOCOL SYNOPSIS

INVESTIGATIONAL PRODUCT	
Name of Investigational Product (IP)	Combination Product: Peregrine System™ Kit (also referred to as Peregrine Kit) Drug Part: Dehydrated Alcohol Injection, USP (also referred to as alcohol, dehydrated alcohol, ethanol, absolute ethanol, ethyl alcohol, or absolute alcohol) Device Part: Peregrine System™ Infusion Catheter (also referred to as Peregrine Catheter)
Name(s) of Active Ingredient(s)	Dehydrated Alcohol Injection, USP
CLINICAL CONDITION(S)/INDICATION(S)	
Hypertension	
Protocol ID	CR0014
Protocol Version and Date	7.0 14 DEC 2021
EudraCT Number	2018-000036-96
Protocol Title	A Phase 2, Multicenter, Blinded, Sham Procedure-Controlled Trial of Renal Denervation by the Peregrine System Kit, in Subjects with Hypertension, in the Absence of Antihypertensive Medications
Short Title	The TARGET BP OFF-MED Trial
Study Phase	Phase 2 (Proof-of-Concept)
PLANNED STUDY PERIOD	
Initiation	MAY 2018
Primary Endpoint Completion	JUN 2021
Study Completion	MAR 2023
Duration	Approximately 5.0 years
STUDY OBJECTIVES AND PURPOSE	
Study Purpose	To obtain an assessment of the efficacy and safety of renal denervation by alcohol-mediated neurolysis using the Peregrine Kit in hypertensive subjects in the absence of antihypertensive medications.
Primary Objective	
 To evaluate the efficacy of renal denervation by alcohol-mediated neurolysis using the Peregrine Kit in hypertensive subjects, when used in the absence of antihypertensive medications, as evaluated by change in mean 24-hour ambulatory systolic blood pressure (SBP) from baseline to 8 weeks post-treatment.

Secondary Objectives	
	
 • To evaluate the acute and chronic safety of renal denervation by alcohol-mediated neurolysis using the Peregrine Kit in hypertensive subjects, up to 2 years post-treatment. • To evaluate the efficacy of renal denervation by alcohol-mediated neurolysis using the Peregrine Kit on blood pressure in hypertensive subjects, up to 1 year post-treatment.
STUDY DESIGN	
Study Type/ Classification/ Discipline	Proof-of-Concept for efficacy (ambulatory blood pressure monitoring [ABPM], office blood pressure)
Control Type	Sham Treatment
Study Indication Type	Treatment
Intervention Model	Parallel
Blinding/Masking	Blinded (The subject, sponsor, and hypertensionist/nephrologist performing the screening and follow-up assessments are blinded. The interventionalist and cath lab staff are unblinded.)

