- Hypotensive crisis
- Symptomatic hypotension that required a change in antihypertensive medications, or medications to increase blood pressure (e.g., persistent syncope, lightheadedness)
- Changes in eGFR from baseline to 8 weeks and 6 months post-treatment.
- Decreases in eGFR >25% from baseline to 8 weeks and 6 months post-treatment.
- Rate of adverse events (AEs) (serious and non-serious), peri-procedurally, at discharge, and at each of the follow-up time points.
- Device success (defined as the ability to insert the Peregrine Catheter into the lumen of the renal artery [target vessel], deploy the guide tubes inside the renal artery, deploy the needles through the arterial wall, deliver the intended dose of alcohol, retract the needles and the guide tubes back in the catheter, and remove the catheter from the access site without any related complications or events)
- Procedure success (defined as device success with freedom from peri-procedural MAEs).

Adverse events will be recorded from the time of signing the informed consent form through the end of study participation. Date of report; date of onset; whether the AE is serious or not; whether the AE is considered an MAE; whether the AE is considered a serious adverse device effect (SADE); whether the AE is considered a suspected unexpected adverse drug reaction; causal relationship (to Peregrine Catheter, study drug [alcohol], and study procedure, separately); action taken; outcome; date recovered/resolved; and date of death (if applicable) of each adverse event will be recorded.

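### SAP 5.8.1 does not specify tabulation of relationship to alcohol, and its definition of treatment-emergent misses an ongoing event with no start date

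*SAP*

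**What the plan says.** **Relationship.** SAP 3.4.3 lists the fields recorded for each adverse event, among them "causal relationship (to Peregrine Catheter, study drug [alcohol], and study procedure, separately"). The protocol synopsis describes a combination product and names the alcohol apart from the catheter: "Drug Part: Dehydrated Alcohol Injection, USP". SAP 5.8.1 then describes causality in three further ways:

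- The definition behind the related-event counts: "Related AEs are those AEs that are recorded as being related to the study procedure/treatment".
- The by-relationship tables, which count events "by relationship to the investigational device or procedure according to both the investigator and the CEC (SAEs only").
- The by-patient listing, which is to include "intensity, relationship to study drug, action taken, and outcome will be presented in the data listings".

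A relationship left blank is handled cautiously: "Events for which the relationship is not recorded will be considered as related for the purpose of the tabular summaries".

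**Treatment-emergent status.** SAP 5.8.1 gives three routes. The first needs a start date and time during or after the procedure. The second is "Have a missing start date, and the stop date is after the procedure". The third needs a start before the procedure and later worsening. I found no rule for missing or partial adverse event dates, and SAP 5.2.3 rules out imputation for endpoints other than the primary one.

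**The concern.** The trial is a proof of concept for a drug-device combination, and its result informs whether to start a pivotal study. A reader of the safety tables will want to see which events were attributed to the active ingredient, which to the catheter and which to the procedure. All three are collected, but the text specifies no table that shows all three.

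The treatment-emergent rule raises a different issue. When the start date is unknown, whether an event is counted depends on whether it has ended. A resolved event is counted and an unresolved one is not. That is an awkward direction for a trial with a safety objective running to 2 years.

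**Working it through.** The plan gives no figure on this point, so there is none to reproduce. The check applies the written rules to every possible combination.

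**1. Relationship.** The inputs are three yes/no attributions (catheter, alcohol, procedure; SAP 3.4.3), giving 2 × 2 × 2 = 8 patterns.

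- Table rule, device or procedure: 6 of the 8 patterns are related. The two that are not are all three no, and alcohol alone.
- Any of the three: 7 of the 8 are related.
- The rules differ on one pattern: alcohol yes, catheter no, procedure no.

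If treatment in the SAP's definition of related includes the alcohol, that pattern is related for the overall summary but not for the by-relationship tables. The SAP would then have two answers for one event.

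The SAP's table list has three event sets by relationship (all, serious, non-serious), each over six periods: 3 × 6 = 18 table titles. The titles say only that they are by relationship. They show how many tables the rule governs, not what columns those tables carry.

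**2. Treatment-emergent status.** The inputs are start date, stop date and worsening, with the three criteria in SAP 5.8.1.

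| Start | Stop | Criterion met | Treatment-emergent as written |
|---|---|---|---|
| Before procedure, no worsening | Any | None | No |
| Before procedure, worsened during or after | After, or ongoing | Third | Yes |
| During or after | After, or ongoing | First | Yes |
| Missing | Before | None | No |
| Missing | After | Second | Yes |
| Missing | None (ongoing) | None, even if it worsens | **No** |

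Worsening does not rescue the last row, because the third criterion needs a start date before the procedure. If a missing start counted as emergent unless the stop date is before the procedure, only the last row would change.

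Partial dates are a related gap. The first criterion asks for a date and a time, so an event on Day 0 with no recorded time cannot be placed before or after the procedure.

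**3. Scale.** The planned arm size is 45 (protocol synopsis). One subject moves a rate by 1/45 = 2.2 percentage points. The documents do not say how many subjects are affected. Taking 1 to 3 per arm as an assumption, with exact (Clopper-Pearson) limits from the beta quantiles Beta(0.025; k, 45 − k + 1) and Beta(0.975; k + 1, 45 − k):

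- k = 1: 2.2% (95% CI 0.1% to 11.8%)
- k = 2: 4.4% (0.5% to 15.1%)
- k = 3: 6.7% (1.4% to 18.3%)

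**The case against.** The strongest reply is that little is lost. An event attributed to alcohol alone is still counted in the summary of "Frequency (number and percentage of subjects) with TEAEs, overall and by MedDRA system organ class and preferred term", and in the severity tables. The treatment is denervation performed with alcohol, so such an event probably also enters the related-event counts. The sham arm receives no alcohol, so the randomised comparison of all treatment-emergent events detects drug harm without any attribution. The table shells, which the SAP says it is to be read with, are not available here and may carry a drug column. On dates, onset is a recorded field, so an event with neither date should be rare, and a programmer might treat an ongoing event as one that stops after the procedure.

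Most of this stands, and it limits the point. Several stronger readings are tempting but not supported:

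- *Harms are removed from the safety tables.* An alcohol-only event loses its attribution in one family of tables. It is not dropped.
- *The listing hides catheter and procedure attribution.* The listing is described as including certain fields, which does not exclude others.
- *Unresolved events are left out in general.* An ongoing event with a known start during or after the procedure meets the first criterion.
- *Undated ongoing events leave every table of major adverse events.* The 30-day analysis in SAP 5.5.1.1 and Table 14.3.5 are not expressly limited to treatment-emergent events.
- *The missing-start rule reverses the cautious rule for a blank relationship.* Where a stop date after the procedure exists, it is itself cautious. It is incomplete for ongoing events.
- *Nearly all undated events began after the procedure.* Collection runs roughly 8 to 12 weeks before and 104 weeks after, so the share would be 104/116 = 90% to 104/112 = 93% if onset were uniform. Nothing in the documents supports uniform onset, and the share says nothing about how many events are affected.

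The reply does not dispose of two things. The written table rule does not name a causality field that the trial collects. And the SAP nowhere says that an ongoing event counts as one that stops after the procedure.

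**Conclusion.** Both defects hold on the text, and both are narrow. In the by-relationship tables, one attribution pattern of eight (alcohol alone) is not shown as related, and the table rule does not match the section's own definition of related. In the treatment-emergent summaries, one combination (no start date, no stop date) is left out. Such an event would remain in the listing of all adverse events.

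The size is unknown and probably small: 2.2 percentage points per affected subject, assuming 45 subjects in the arm. The primary endpoint is not touched. The first defect assumes that device does not include the alcohol, as the protocol's split into drug part and device part suggests, and that the unseen shells follow the SAP text. If the shells already carry an alcohol column, the text still has to be brought into line with them. The second assumes that the three criteria are programmed as written. The change should be made because it is cheap and uses data already collected.

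**What to change.** In SAP 5.8.1 and 5.8.1.1:

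1. Use one definition of related throughout: related to the catheter, the alcohol or the procedure.
2. Tabulate relationship separately for each of the three, plus any of the three, and show all three in the by-patient listing.
3. State how the rule for a blank relationship works with three fields, including in the sham arm, which receives no alcohol infusion.
4. Replace the second treatment-emergent criterion with: an event with a missing start date is treatment-emergent unless its stop date is before the procedure.
5. Add: an event with a partial start date, or a Day 0 event without a time, is treatment-emergent unless the known part places it before the procedure.

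The cost is SAP wording, table shells and programming; no new data are needed. The downside is that a few events of unknown onset that began before the procedure may be counted as treatment-emergent.
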